1.3 SCHEDULE OF ACTIVITIES

The schedule of the activities is provided in [Table 1](#) to [Table 3](#).

Table 1 Schedule of Activities – Main Table

Day	Screening up to Day-28	Treatment Period 1 & Washout period of 9 Days ± 1 Day up maximum of 18 Days								Treatment Period 2														Follow-up Visit (15 to 20 days after last itraconazole)			
		Day -1	Day 1	Day 2	Day 3	Day 4	Day 5	Day 6	Day 8	Day -1	Day 1	Day 2	Day 3	Day 4	Day 5	Day 6	Day 7	Day 8	Day 9	Day 10	Day 11	Day 12	Day 13	Day 14	Day 15	Day 16	
Assessments																											
Informed Consent	x																										
Demography	x																										
Medical History	x																										
Physical Examination^a	x	x								x													x				x
In house Period		x	x	x	x	x					x	x	x	x	x	x	x	x	x	x	x	x	x	x			
Discharge from the unit							x																x				
Ambulatory Visit								x	x	x														x	x	x	x
Vital Signs^b	x	x	x	x	x	x	x	x	x	x	x	x	x	x	x	x	x	x	x	x	x	x	x	x	x	x	
12-Lead ECG^c	x	x	x	x	x	x	x	x	x	x	x	x	x	x	x	x	x	x	x	x	x	x	x	x	x	x	
Serology	x																										
Pregnancy Test^d	x	x																									
Hormone Panel^e	x	x																									
Alcohol Breath Test	x	x							x																		
Urine Drugs of Abuse	x	x							x																		
Urinalysis	x	x			x				x	x					x		x		x					x	x		
Blood Chemistry	x	x		x						x	x				x		x		x					x	x		
Hematology	x	x		x						x	x				x		x		x					x	x		
Coagulation	x	x																									
RO7017773 Administration^f																											
Itraconazole Administration^g										x	x	x	x	x	x	x	x	x	x	x	x	x	x	x	x		
Standard Meal^h	x	x ⁱ								x	x	x	x	x ⁱ	x	x	x	x	x	x	x	x	x	x	x		
Itraconazole and metabolites PK sample										x					x	x	x	x	x	x	x	x	x	x	x	x	
Clinical Genotyping		x																									
C-SSRS	x	x						x			x			x										x			
Adverse Events	x	x	x	x	x	x	x	x	x	x	x	x	x	x	x	x	x	x	x	x	x	x	x	x	x	x	
Concomitant medications	x	x	x	x	x	x	x	x	x	x	x	x	x	x	x	x	x	x	x	x	x	x	x	x	x	x	

PK = Pharmacokinetic

Table 1 Schedule of Activities – Main Table (cont.)

- a) Physical examination will include body weight at screening and follow-up, and height at screening when body mass index (BMI) will be derived.
- b) Vital signs will include blood pressure, pulse rate, and (at selected time points) body temperature. Vital sign measurements will be taken after the participant has rested in a supine position for at least 5 minutes.

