2.3 BENEFIT/RISK ASSESSMENT

This study is being conducted to evaluate the PK of RO7017773 with and without concomitant administration of itraconazole to investigate the effects of inhibition of CYP3A on RO7017773 exposure.

In order to minimize the number of participants required in the study, a within-subject study design has been chosen and an open-label, one-sequence design was selected.

Itraconazole is generally well tolerated. The itraconazole dosing regimen in this study is consistent with the prescribing recommendations for itraconazole ([SmPC](#)). Approved dosing regimens for the treatment of fungal infections include doses up to 200 mg BID

for periods of up to one year. Itraconazole doses of 200 mg QD or BID are also commonly used in DDI studies to ensure adequate CYP3A inhibition (Ke et al 2014; Liu et al 2015).

There is extensive clinical experience of the use of itraconazole and the potential clinical risks are well characterized. While some side effects occur frequently (e.g., headache, abdominal pain, and nausea), these generally do not require any medical intervention and side effects requiring treatment tend to occur rarely. There are a number of contraindications and precautions within the approved itraconazole prescribing information, but potential risks will be minimized by enrolling only healthy participants and specifically excluding people for whom the drug is contraindicated (e.g. history of heart failure).

Itraconazole PK will be measured when given alone and concomitantly with RO7017773 to ascertain that the PK concentrations of itraconazole ensure maximal CYP3A4 inhibition. Participants will be kept in the clinical unit under continuous medical supervision and monitoring for 3 days after single administration of RO7017773 alone and one week after RO7017773 administration in combination with itraconazole. They will remain in the clinical unit up to 3 days after the administration of the last dose of itraconazole.

More detailed information about the known and expected benefits in the context of potential risks and reasonably expected AEs of RO7017773 and itraconazole are provided in the [Investigator's Brochure](#) and in the [SmPC](#), respectively.

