In Period 1, participants will be administered a single oral dose of RO7017773 alone in fed state. In Period 2, after a wash-out period of 10 days, participants will receive multiple doses of itraconazole in fed state for 9 days and be administered [REDACTED] RO7017773 [REDACTED] in combination with itraconazole [REDACTED].

Healthy participants will be admitted to the clinical unit on Day -1 of Period 1. An oral dose of [REDACTED] RO7017773 will be administered alone, 30 minutes after starting a standardized breakfast on the morning of Day 1 of Period 1. Participants will be discharged on the morning of Day 4 after all assessments have been completed. They will return to the clinical unit for 3 ambulatory visits at Day 5, Day 6, and Day 8 for PK sampling and safety monitoring.

After a wash-out period of 10 days, participants will be admitted to the clinical unit on Day -1 of Period 2 and will remain in-house until the morning of Day 12. They will be administered 200 mg of itraconazole BID (12 hours apart) *on Day 1 and 200 mg of itraconazole QD from Day 2 to Day 9* in Period 2. Itraconazole will be administered as oral capsules containing 200 mg every 12 hours (BID), 30 minutes after starting a standardized breakfast in the morning and after a standardized dinner in the evening *on Day 1 only and on Days 2 to 9 oral capsules containing 200 mg once a day (QD), 30 minutes after starting a standardized breakfast in the morning*. On the morning [REDACTED]

[REDACTED] RO7017773 will be administered to each participant in combination with the morning dose of itraconazole. Participants will be discharged on the morning of Day 12 after all assessments have been completed. They will return to the clinical unit for 4 ambulatory visits at Day 13, Day 14, Day 15, and Day 16 for PK sampling and safety monitoring.

Participants will visit the clinical research unit for a safety follow-up visit 15 to 20 days after the last dose of itraconazole.

[REDACTED] Similarly, safety data will be collected in Period 1 and Period 2 in order to assess the effect of itraconazole on the safety profile of RO7017773.

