4.1.1 Length of the Study

The total duration of the study for each participant will be up to 10 weeks, divided as follows (see also Section 1.3, Figure 1):

- **Screening:** Up to 4 weeks
- **In-clinic and dosing Period 1:** Day -1 to Day 4 with a single oral dose of [REDACTED] RO7017773 administered on Day 1.
- **Ambulatory visit Period 1:** Day 5, 6 and 8 (PK sampling and safety monitoring)
- **Washout Period:** Approximately 9 days *to a maximum of 18 days (± 1 Day)* (i.e., between Day 1 of Period 1 and Day -1 of Period 2).
- **In-clinic and dosing Period 2:** Day -1 to Day 12 with multiple oral dose administrations of itraconazole (200 mg BID *Day 1 and 200 mg QD Days 2 to Day 9*) from Day 1 to Day 9 and co-administration of [REDACTED] RO7017773 with itraconazole on the morning [REDACTED].
- **Ambulatory visit Period 2:** Day 13, Day 14, Day 15, and Day 16 (PK sampling and safety monitoring).
- **Follow-up visit:** 15 to 20 days after the last dose of itraconazole.

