11.1. Adverse events

Adverse events, including pre-treatment serious events only, will be recorded from the time of consent through 15 to 20 days after the end of treatment period.

Adverse events will be coded according to MedDRA Version 21.1.

A treatment-emergent adverse event (TEAE) is an adverse event that occurs on or after the first IMP administration of each period or that was present prior to dosing but was exacerbated on or after the first IMP administration of each period.

Adverse events will be summarised in tables as follows [overall and by System Organ Class (SOC) and Preferred Term (PT)]:

- Number and percentage of subjects with at least one adverse event and number of occurrences of an adverse event by treatment group (before any treatment and after first intake of each treatment) and overall,
- Number and percentage of subjects with at least one TEAE and number of occurrences of a TEAE by treatment group,

- By intensity, with the number and percentage of subjects with at least one TEAE and number of occurrences of a TEAE by treatment group,
- By causality (to RO7017773 alone, to itraconazole alone and to both RO7017773 and itraconazole), with the number and percentage of subjects with at least one TEAE and number of occurrences of a TEAE by treatment group.

If there are only a few adverse events (≤ 10), only a listing will be generated.

All adverse events reported in the electronic Case Report Form (eCRF) will be listed with the SOC, the PT and the investigator's verbatim. All TEAEs will also be listed with the SOC and the PT. An additional listing will be provided for AEs leading to death and other serious and significant AEs (SAEs or AEs leading to study withdrawal).

Note:

- i. In the descriptive tables, the number of subjects with at least one adverse event/TEAE for a given PT will also correspond to the number of adverse events/TEAEs whatever the number of occurrences during the studied period.
- ii. In case of a change of intensity or causality for an event during the same treatment period, the intensity will be the highest recorded intensity and the causality will be the highest likelihood recorded.
- iii. A treatment-emergent AE will be associated with the treatment group of the current period if this AE starts between the first IMP administration of the current period and the first IMP administration of the next period.

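### At the nominal washout, TEAEs are compared over about 10 days after RO7017773 alone and 19 to 25 days after the combination, and no planned table equalises time at risk

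*SAP*

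**What the plan says.** SAP 11.1 plans crude TEAE summaries, overall and by SOC and PT: "Number and percentage of subjects with at least one TEAE and number of occurrences of a TEAE by treatment group". The intensity and causality tables use the same measure. SAP 6 names three groups for AEs: RO7017773 alone, itraconazole alone, and RO7017773 + itraconazole. Note iii of SAP 11.1 assigns an event to the current period's group "if this AE starts between the first IMP administration of the current period and the first IMP administration of the next period". Period 2 has no next period, so its window runs until AE collection ends.

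The documents give two ends of collection. Protocol 8.3.1 stops 14 days after the last dose of study treatment. SAP 11.1 records events through 15 to 20 days after the treatment period, in line with a follow-up visit "15 to 20 days after the last dose of itraconazole" (Protocol 4.1.1).

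The Schedule of Activities (Protocol 1.3) gives a "Washout period of 9 Days ± 1 Day up maximum of 18 Days". Protocol 4.1.1 explains what it spans: "i.e., between Day 1 of Period 1 and Day -1 of Period 2".

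On purpose, Protocol 4.1 says that "safety data will be collected in Period 1 and Period 2 in order to assess the effect of itraconazole on the safety profile of RO7017773". On supervision, Protocol 2.3 keeps participants in the unit for "3 days after single administration of RO7017773 alone and one week after RO7017773 administration in combination with itraconazole".

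**The concern.** Safety of RO7017773 alone and in combination is a secondary objective, and the AE columns are the planned way to look at it. A crude percentage with at least one event rises with the length of observation. If one column is observed for longer, background events alone push it up, and the excess can be read as an effect of itraconazole on tolerability.

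Nothing planned offsets this. Laboratory, vital-sign and ECG summaries are by measurement time (SAP 11.2 and 11.3), but the AE tables are not aligned in time. Listings count study days from the first study drug administration (SAP 6), so a reader would have to work out time since the Period 2 RO7017773 dose. With 14 to 18 participants, two extra people with a background event visibly change a percentage.

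**Working it through.** The documents state no window length, ratio or background AE rate, so there is no planned figure to reproduce. The check is day arithmetic plus an assumed background rate.

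**Inputs**
- Washout to Period 2 Day -1: 9 days (8 to 10 with ±1), maximum 18, or 19 if ±1 applies there too (Protocol 1.3 and 4.1.1).
- No Day 0, so Day -1 to Day 1 is one day (SAP 6).
- RO7017773 in Period 2: Day 4. The dosing text is redacted; this is inferred from the pre-dose and hourly time points on Day 4 in SAP 11.3.
- Last itraconazole dose: Period 2 Day 9 (Protocol 4.1, SAP 3).

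**Windows**
- RO7017773 alone = washout + 1. Nominal: 9 + 1 = 10 days, agreeing with the 10-day wash-out in SAP 3. At the maximum: 18 + 1 = 19 days (20 if 19 + 1).
- Combination, protocol end: (9 + 14) − 4 = 19 days.
- Combination, SAP end: (9 + 15) − 4 = 20 to (9 + 20) − 4 = 25 days.
- Itraconazole alone: Day 1 to Day 4 = 3 days.

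**Ratio of combination to RO7017773-alone window**

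| Washout (days) | RO7017773 alone (days) | Protocol end (19) | SAP end (20 to 25) |
|---|---|---|---|
| 8 | 9 | 2.11 | 2.22 to 2.78 |
| 9 (nominal) | 10 | 1.90 | 2.00 to 2.50 |
| 10 | 11 | 1.73 | 1.82 to 2.27 |
| 18 | 19 | 1.00 | 1.05 to 1.32 |
| 19 | 20 | 0.95 | 1.00 to 1.25 |

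**Other readings of the assignment rule, nominal washout**
- All of Period 2 counted as combination from Day 1: 22 to 28 days against 10, ratio 2.2 to 2.8.
- IMP read as RO7017773 only, as the protocol synopsis defines it: Period 1 runs to Period 2 Day 4, 10 + 3 = 13 days, ratio 19/13 to 25/13 = 1.5 to 1.9. At an 18-day washout this becomes 22 days and the ratio 0.86 to 1.14.

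**Effect on the percentages with no drug effect.** Assume a constant background rate r: P(at least one TEAE) = 1 − exp(−r × days).

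| r per participant-day (assumed) | 10 days | 19 days | Ratio | 25 days |
|---|---|---|---|---|
| 0.01 | 9.5% | 17.3% | 1.82 | 22.1% |
| 0.02 | 18.1% | 31.6% | 1.74 | 39.3% |
| 0.05 | 39.3% | 61.3% | 1.56 | 71.3% |

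At r = 0.02 with 14 participants, 10 versus 19 days means 14 × 0.181 = 2.5 against 14 × 0.316 = 4.4 participants. At an 18-day washout with the protocol end, both windows are 19 days and the difference is nil. Expected counts of occurrences scale directly with the window ratio.

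**Listing-only rule.** SAP 11.1 produces only a listing if there are 10 or fewer AEs. Background events over 10 + 3 + 19 = 32 days in 14 participants (448 participant-days): 4.5 expected at 0.01 and 9.0 at 0.02. In 18 participants (576 participant-days): 5.8 and 11.5.

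**The case against.** The other side has several fair points.

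- **Not fixed by design.** A reader might infer that the windows differ two-fold by design and that the combination must look worse. The documents do not support that: they allow a washout at which the windows are equal or slightly reversed, and they do not say which washout will be typical. This stands.
- **Size.** A spurious difference of up to 2.3-fold might also be inferred. It needs the latest SAP follow-up day (25 days) and the lowest of the three assumed rates (22.1% / 9.5%). With the protocol end it is 1.6- to 1.8-fold. This stands.
- **No test is planned.** Protocol 9.1 calls the study exploratory, with no formal hypotheses. Causality is assessed for each drug separately (Protocol Appendix 2, section 3.2) and tabulated, and onset times are available. That helps interpretation, but open-label causality judgements do not equalise time at risk.
- **The tables may not appear.** At low background rates the listing-only rule could apply. True, although drug-related events also count towards the threshold.
- **The split is unclear.** The all-AE table refers to the first intake of each treatment, which hints at a cut at the RO7017773 dose, while note iii assigns by period. The uncertainty is real, but at the nominal washout every reading leaves the combination observed for longer.
- **A short window could mislead.** Itraconazole continues to Day 9, and Protocol 4.3 says it may prolong RO7017773 elimination. Part of the longer window is therefore real exposure, and a 7-day table alone could miss later events. This stands and limits the remedy.

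**Conclusion.** The concern holds in a bounded form. At the nominal washout the combination column is observed 1.9 to 2.5 times as long as the RO7017773-alone column. At the maximum washout the ratio is about 0.95 to 1.3. Time at risk therefore depends on scheduling and usually favours RO7017773 alone. With no drug effect, 10 versus 19 days produces an apparent 1.6- to 1.8-fold difference in the percentage with a TEAE.

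This rests on RO7017773 being given on Period 2 Day 4, on a cut between groups at that dose, and on a constant background rate of 0.01 to 0.05 per day, which the documents do not give. The contrast is descriptive, and the primary PK analysis is unaffected. It is still worth correcting, because these columns are what the protocol offers for judging itraconazole's effect on the safety profile.

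**What to change.** In SAP 11.1:

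1. State how Period 2 TEAEs are divided between itraconazole alone and RO7017773 + itraconazole, with the cut at the Period 2 RO7017773 dose.
2. Reconcile the end of AE collection with Protocol 8.3.1.
3. Add one TEAE table restricted to onset within the same interval after the RO7017773 dose in each period, for example 168 h (Period 1 Days 1 to 8; Period 2 Days 4 to 11 if dosing is on Day 4).
4. Keep the full-window tables and show participant-days at risk for each column.
5. Use the equal-window table as the main like-for-like comparison, and interpret it together with the full-window tables.

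The cost is SAP wording and one extra table from data already collected. SAP 1 has the plan signed before database lock, so this can be specified in advance. There are two downsides. Later-onset events under prolonged exposure appear only in the full-window tables. Supervision within the 7 days still differs: Period 1 is in-house to Day 4 with visits on Days 5, 6 and 8, while Period 2 Days 4 to 11 are entirely in-house (Protocol 4.1).

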11.2. Clinical laboratory data

The following clinical laboratory parameters will be measured (see section 14.1):

- at screening visit,
- in Period 1: on Day -1, Day 3 and Day 8,
- in Period 2: on Day -1, Day 4, Day 7, Day 10 and Day 16,
- at follow-up visit.

Haematology parameters will be listed and grouped as follows:

- Red blood cells: erythrocytes ($10^{12}/L$), hematocrit (ratio) and hemoglobin (g/L).
- White blood cells: basophils ($10^9/L$), eosinophils ($10^9/L$), leukocytes ($10^9/L$), lymphocytes ($10^9/L$), monocytes ($10^9/L$) and neutrophils ($10^9/L$).
- Other parameters: platelets ($10^9/L$).

Blood chemistry parameters will be listed and grouped as follows:

- Liver function: alanine aminotransferase (IU/L), alkaline phosphatase (IU/L), aspartate aminotransferase (IU/L), bilirubin ($\mu\text{mol}/L$), direct bilirubin ($\mu\text{mol}/L$).
- Renal chemistry: creatinine ($\mu\text{mol}/L$) and urea (mmol/L).
- Electrolytes: bicarbonate (mmol/L), calcium (mmol/L), chloride (mmol/L), phosphate (mmol/L), potassium (mmol/L) and sodium (mmol/L).
- Metabolism parameters: cholesterol (mmol/L), glucose (mmol/L), lactate dehydrogenase (IU/L), triglycerides (mmol/L) and urate ($\mu\text{mol}/L$).
- Other proteins: albumin (g/L) and protein (g/L).

Urinalysis parameters will be listed and grouped as follows:

- Planned urinalysis parameters: dipstick determination of erythrocytes, glucose, leukocytes, nitrite and protein, pH and specific gravity.

- Direct microscopy (in case of abnormal urinalysis parameters and in the listing only): cytology (erythrocytes, leukocytes, epithelial cells, granular casts and hyaline casts), bacteria (/uL) and crystals (calcium phosphate crystals, calcium oxalate crystals and monosodium urate crystals).

For haematology and blood chemistry, raw data and changes from baseline will be described by treatment group and measurement time.

For urinalysis, raw data (planned parameters) will be described by summary statistics or frequency tables by treatment group and measurement time.

For haematology, blood chemistry and urinalysis, values higher or lower than the laboratory reference range (H, L) will be listed.

Values (raw data and changes from baseline) will be listed and data out of normal ranges will be flagged with clinical significance information.

Urinalysis values will be listed, including direct microscopy, if any.

11.3. Other safety parameters

11.3.1. Vital signs data

Supine systolic and diastolic blood pressure (mmHg) and heart rate (HR) (beats/min) will be measured (see section 14.1):

- at screening visit,
- in Period 1: on Day -1, Day 1 at pre-dose, H1, H2, H5, H6 and H8, Day 2, Day 3, Day 4, Day 5 and Day 8,
- in Period 2: on Day -1, Day 1, Day 4 at pre-dose, H1, H2, H5, H6, H8, Day 5, Day 6, Day 8, Day 9, Day 12 and Day 16,
- at follow-up visit.

Body temperature (C°) will be measured (see section 14.1):

- at screening visit,
- in Period 1: on Day -1, Day 1 at pre-dose, H1 and H6, and Day 2,
- in Period 2: on Day -1, Day 1, Day 4 at pre-dose, H1 and H6, and Day 5,
- at follow-up visit.

Raw data and changes from baseline will be described by treatment group and measurement time.

Values higher or lower than the normal range will be listed. The normal ranges are the following:

PARAMETER	LOWER NORMAL VALUE	UPPER NORMAL VALUE
Supine HR	≤ 40 beats/min	≥ 100 beats/min
Supine SBP	≤ 90 mmHg	≥ 140 mmHg
Supine DBP	≤ 50 mmHg	≥ 90 mmHg

Values (raw data and changes from baseline) will be listed and data out of normal ranges will be flagged with clinical significance information.

11.3.2. Electrocardiogram data

Standard 12-lead electrocardiogram (ECG) parameters (including heart rate (beats/min), PR interval (msec), RR interval (msec), QRS duration (msec), QT interval (msec) and Fridericia QTc interval (msec)) and ECG abnormalities will be recorded in triplicate (see section 14.1):

- at screening visit,
- in Period 1: on Day -1, Day 1 at pre-dose, H1, H2, H5, H6 and H8, Day 2, Day 3, Day 4, Day 5 and Day 8,
- in Period 2: on Day -1, Day 1, Day 4 at pre-dose, H1, H2, H5, H6, H8, Day 5, Day 6, Day 8, Day 9, Day 12 and Day 16,
- at follow-up visit.

The mean of the triplicate ECGs will serve as analysable data.

Only interpretable ECGs will be analysed.

Raw data and changes from baseline (except for ECG abnormalities) will be described by treatment group and measurement time.

Values [raw data/ECG abnormalities and changes from baseline)] will be listed.

11.3.3. Physical examination

A complete physical examination will be measured (see section 14.1):

- at screening visit,
- in Period 1: on Day -1,
- in Period 2: on Day -1 and Day 12,
- at follow-up visit.

Weight will be measured at screening and follow-up visits.

Abnormal results as well as all individual data of physical examination will be listed.

Raw data of weight and BMI will be described overall and listed.

11.3.4. Alcohol breath test and urine drug of abuse

Alcohol breath test and urine drug of abuse will be measured (see section 14.1):

- at screening visit,
- in Period 1: on Day -1,
- in Period 2: on Day -1.

Positive results as well as all individual data of alcohol breath test and urine drug of abuse will be listed.

